## **13. Pharmaceutical Information**

### **13.1. Investigational Agent-Daratumumab**

Daratumumab as a drug product is a colorless to yellow liquid concentrate. It is presented at a target concentration of 20 mg/mL in a 6R or 25R vial with a nominal fill volume of 5 mL or 20 mL, respectively. It is intended for administration by the IV route after dilution in a sterile, pyrogen-free physiological saline solution (0.9% NaCl) provided by the investigation site. The

diluent will be a commercially available product approved by the competent authority of the relevant country.

### **13.2. Availability of study drugs**

Daratumumab is an investigational agent supplied to investigators by Janssen. The study drug will be open-label with labeling fulfilling all requirements specified by governing regulations. Ibrutinib will be used per its FDA labeling and will be obtained through commercial mechanisms via the subject's insurance.

### **13.3. Daratumumab Accountability**

Daratumumab Inventory Records – The investigator, or a responsible party designated by the investigator, will maintain a careful record of the inventory and disposition of all agents received from Janssen on a Drug Accountability Record Form (DARF).

## **14. Measurement of Effect**

During this study, participants will be evaluated every 4 weeks +/- 1 week for Cycles 1-12 and then every 12 weeks +/- 2 weeks for Cycles 13-26 during combination treatment to complete 2 years of treatment. Subjects that complete combination treatment will be evaluated on single agent ibrutinib every 12 weeks +/- 2 weeks for an additional 1 year until study completion. Subjects will be assessed for efficacy according to the response criteria in Section 9.1 adopted by the Third International Workshop on WM.

### **14.1. Response Criteria**

Subjects will be evaluable for a response if they have completed 2 Cycles of combination induction treatment (Weeks 1-8). See **Appendix C** for summary of response criteria.

**Complete Response (CR):** A complete response (CR) is defined as having resolution of WM related symptoms, normalization of serum IgM levels with complete disappearance of IgM paraprotein by immunofixation, and resolution of any adenopathy or splenomegaly. A complete response requires reconfirmation demonstrating normal serum IgM levels, and absence of IgM paraprotein by immunofixation by a measurement repeated at least 2 weeks later.

**Very Good Partial Response (VGPR):**  $\geq 90\%$  reduction in serum IgM levels, or normalization of serum IgM levels.

**Partial Response (PR):**  $\geq 50\%$  reduction in serum IgM levels

**Minor Response (MR):** 25-49% reduction in serum IgM levels

**Progressive Disease (PD):** >25% increase in serum IgM level occurs with an absolute increase of at least 500mg/dL from the lowest attained response value, or progression of clinically significant disease related symptoms. Reconfirmation of the initial IgM increase is required when the IgM is the sole criterion for progressive disease. For participants on active therapy who are on a drug hold for > 7 days an increase in serum IgM will not be considered progression if in the investigators opinion it is secondary to the drug hold. Subjects will be allowed reinitiation of drug. If after four consecutive weeks on active therapy there is no decrease in IgM, subjects will be considered to have progressive disease. If there is clinical benefit continuation on trial will be considered. Cases such as this should be discussed with the study sponsor. An increase of 1cm in any axis for adenopathy or 2 cm in the craniocaudal axis of the spleen will be considered progression. Development of central nervous system or transformation will be considered progressive events.

**Stable Disease (SD):** <25% change in serum IgM levels in the absence of new or increasing adenopathy, splenomegaly or other signs of active WM.

**Overall Response:** Includes MR, PR, VGPR, CR

**Major Response:** Includes PR, VGPR, CR

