**Methodology:**

We propose a multi-center, two cohort Phase II clinical trial to investigate the effectiveness of adding daratumumab to ibrutinib in WM patients. Cohort A will consist of patients who are ibrutinib naïve and appropriate for ibrutinib based treatment. Cohort B will consist of patients who have achieved a response plateau less than a complete remission (CR) on single agent ibrutinib.

Subjects in Cohort A will be identified by their treating physician and eligible for enrollment if they are treatment naïve or ibrutinib naïve after prior therapy and eligible for ibrutinib based treatment. Subjects in Cohort B will be identified by their treating physician and eligible for enrollment if they have had at least 6 months of exposure to single agent ibrutinib and demonstrate an IgM response plateau defined by two IgM measurements, at least 8 weeks apart that have changed <15% from the previous mark. In Cohort B response assessment will be measured from initial IgM level prior to ibrutinib initiation. Enrolled subjects will be prescribed commercial ibrutinib, 420mg PO daily. The investigational agent, daratumumab will be administered based on FDA approved dosing in multiple myeloma (16mg/kg) with 8 weekly induction treatments during Cycles 1 and 2, followed by every other week dosing for Cycles 3-6, then monthly dosing from Cycle 7 until Cycle 24 at which point they will continue with ibrutinib as monotherapy until Cycle 52 (4 years total) which is the predefined study completion for enrolled subjects at which point they will complete follow-up.

Study visits and response assessments with IgM measurements will occur with each cycle for the first year then every three cycles after cycle 13. Subjects with measurable extramedullary disease will have CT scans every 6 cycles until radiographic CR. Patients will be considered evaluable for response if they completed the initial 8 weeks of daratumumab induction therapy and evaluable for toxicity if receiving one dose of daratumumab. Patients will continue on combination therapy for 2 years or until disease progression or unacceptable toxicities at which point patients will come off trial. Patients achieving a CR after two years of combination therapy will be given an option to continue with single agent commercial ibrutinib.

Subjects to be enrolled	24 total subjects, 12 in Cohort A and 12 in Cohort B
Study Duration	6 years
Accrual period	2 years

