Study visits and response assessments with IgM measurements will occur day 1 of each cycle through cycle 13 then day of 1 every three cycles after the first year on treatment. Subjects with measurable extramedullary disease will have CT scans every 6 months while on study or until radiographic CR at which point they will occur at the discretion of the investigator. Patients will be considered evaluable for response if they completed the initial 8 weeks of daratumumab induction therapy. Response assessment in Cohort B will be measured from the IgM level recorded prior to ibrutinib initiation. Subjects will continue on combination therapy for 2 years until disease progression or unacceptable toxicities at which point patients will stop daratumumab therapy and come off study. All subjects will be followed for 1 year after completing combination therapy unless they come off study early for other reasons. Subjects achieving a CR will be given an option to continue with single agent commercial ibrutinib or stop all therapy.

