arm. In total 31 patients were accrued to the ibrutinib only arm between August 2014 and February 2015. Thirteen (42%) of the 31 patients had high-risk disease per the International Prognostic Scoring System Waldenström Macroglobulinemia. At a median follow-up of 18.1 months, the overall response rate was 90% with 71% of patients attaining a major response. The estimated 18 month PFS was 86% and the 18 month OS was 97%. Baseline hemoglobin of 10.3 g/dL increased to 11.4 g/dL after 4 weeks of treatment. Grade 3 or greater adverse events were neutropenia (13%), hypertension (10%), and anemia, thrombocytopenia, and diarrhea (6%) each. Serious adverse events occurred in 10 patients (32%) and most often related to infections. Five patients discontinued ibrutinib; 3 due to progression and 2 due to adverse events.

Given the results of the Phase II data the Federal Drug Administration (FDA) gave accelerated approval for the treatment of patients in both treatment naïve and relapsed refractory settings.

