### **Ibrutinib Lead-In (Cohort A only)**

The ibrutinib lead-in will apply to subjects in **Cohort A only** and will consist of one cycle of continuous daily ibrutinib monotherapy (Cycle -1) prior to beginning combination treatment as part of the induction phase.

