### **12.4.1. Daratumumab Dose Delay Management**

If dosing is delayed for either toxicity or other non-toxicity related issue then the following schedule should be followed during the specific phases of daratumumab treatment.

During the induction phase (Cycles 1 and 2) if the dose is delayed  $>3$  days then that week's dose will be considered missed and treatment will commence the following week. If a missed dose occurs during induction, then that dose will not be made up and subjects will remain on schedule.

During the consolidation phase (Cycles 3-6) if a dose is held greater than 1 week, then the next dose given should be the scheduled Day 15 dose.

During the maintenance phase Cycle 7 and beyond if a dose is delayed greater than 2 weeks then it should be resumed with the subsequent cycle on day 1.

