#### 14.2. Time to Event Definitions

**Duration of Response (DoR):** The duration of overall response is measured from the time measurement criteria are met for Minor response or better until the first date that recurrent or progressive disease is objectively documented (taking as reference for progressive disease the smallest IgM measurements recorded since the treatment started).

**Progression-Free Survival (PFS):** PFS is defined as the duration of time from start of treatment to time of progression or death.

**Overall Survival (OS):** OS is defined as the duration of time from start of treatment to time of death or last follow-up.

**Time to Progression (TTP):** TTP is defined as the time to tumor progression as defined in Section 9.1. If the subject has not progressed, then data will be censored at the last study visit at which a tumor assessment was performed.

**Evaluation of toxicity.** All patients will be evaluable for toxicity from the time of their first treatment with Daratumumab.

**Evaluation of response.** All patients included in the study will be assessed for response to treatment if they have completed Cycle 2.

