## **16. Statistical Considerations**

Because this is a pilot study, no formal sample size/power calculation is required. However, with 12 patients each cohort, an exact binomial (Clopper-Pearson) 95% confidence interval for the toxicity proportion (i.e., primary endpoint) can be constructed to have a width of approximately 45.0% (1.6%, 46.5%) (i.e., separate confidence interval for each cohort). This calculation assumes that the toxicity proportion for the incidence of non-hematologic Grade  $\geq 3$  events will be no greater than 15% in either cohort. Secondary endpoints include major response (PR/VGPR/CR), percentage of patients with deepening of response in Cohort B, duration of response, and time to progression. Given this is a pilot study with low subject enrollment and lack of power, analysis of outcomes will remain descriptive without comparison analyses between cohorts. The toxicity and major response proportions will be calculated for each cohort along with exact binomial (Clopper-Pearson) 95% confidence intervals. Duration of response and time to progression will be descriptively reported for each cohort. Assuming adequate follow-up time, Kaplan-Meier survival analysis will be used to assess progression-free survival (PFS) and overall survival (OS) in each cohort. All p-values will be two-sided with statistical significance evaluated at the 0.05 alpha level. Ninety-five percent confidence intervals for 1) the toxicity proportion, 2) the major response proportion, and 3) median PFS/OS-time and PFS/OS proportions, will be calculated to assess the precision of the obtained estimates. All analyses will

be performed in SAS Version 9.4 (SAS Institute, Inc., Cary, NC) and Stata Version 15.0 (StataCorp, College Station, TX).

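### Response is evaluable only in patients who complete the 8-week induction, and Section 16 names no response denominator, so early leavers can drop out of the reported rate

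*Combined protocol and SAP*

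**What the plan says.** Four places tie response evaluation to finishing induction. The synopsis (Methodology) reads "Patients will be considered evaluable for response if they completed the initial 8 weeks of daratumumab induction therapy", and Section 1 repeats the rule. Section 14.1 reads "Subjects will be evaluable for a response if they have completed 2 Cycles of combination induction treatment (Weeks 1-8", and Section 14.2 reads "All patients included in the study will be assessed for response to treatment if they have completed Cycle 2".

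Section 16 gives the analysis: "The toxicity and major response proportions will be calculated for each cohort along with exact binomial (Clopper-Pearson) 95% confidence intervals". It does not say whether the response denominator is enrolled, treated or evaluable patients. It gives no all-treated response rate and no rule for patients who leave early.

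Other provisions that bear on the point:

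- The toxicity set is wider: one daratumumab dose is enough (synopsis; Section 14.2).
- Cohort A has a lead-in that "will consist of one cycle of continuous daily ibrutinib monotherapy (Cycle -1) prior to beginning combination treatment". A patient lost during it is in neither the response set nor the toxicity set.
- For Cohort B, Section 1 states: "Response assessment in Cohort B will be measured from the IgM level recorded prior to ibrutinib initiation".
- PFS and OS run from the start of treatment with no completion condition (Section 14.2).

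**The concern.** A response set limited to completers is selected by what happens after treatment starts. Patients who stop in the first two months for toxicity, progression or death are unlikely to be a random sample, and the Section 22 stopping rule itself anticipates discontinuation in that window. If they leave the denominator, the rate describes those who tolerated induction and did not progress during it. It is not the rate among patients given the combination.

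The direction depends on who leaves. Losing non-responders raises the rate. Losing a patient who already meets a response category lowers it. This is a real possibility in Cohort B, where patients enter on an ibrutinib plateau and are scored against pre-ibrutinib IgM, so some may count as responders before the first daratumumab dose.

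The stake is a reported proportion in cohorts of 12, where one patient matters. Response and PFS/OS could also describe different patients within one report.

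**Working it through.** **Method check on the plan's own figure.** Section 16 gives an exact 95% interval of 1.6% to 46.5% (width about 45.0%) for a toxicity proportion of 15% with 12 patients. The Clopper-Pearson limits are Beta(0.025; x, n−x+1) and Beta(0.975; x+1, n−x). With n = 12 and x = 12 × 0.15 = 1.8 they give 1.57% to 46.54%, width 44.97%. The figure reproduces. The plan states no precision figure for response.

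**Effect of the denominator.** Eight major responders of 12 treated is an assumption for illustration. The same interval formula gives:

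| Patients dropped | Rate | 95% CI |
|---|---|---|
| None | 8/12 = 66.7% | 34.9 to 90.1 |
| One non-responder | 8/11 = 72.7% | 39.0 to 94.0 |
| Two non-responders | 8/10 = 80.0% | 44.4 to 97.5 |
| One responder | 7/11 = 63.6% | 30.8 to 89.1 |
| Two responders | 6/10 = 60.0% | 26.2 to 87.8 |

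The point estimate moves by between 60.0 − 66.7 = −6.7 and 80.0 − 66.7 = +13.3 percentage points. The intervals overlap almost entirely.

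**How likely is a loss?** The documents give no early-loss rate for the combination. The nearest figure is for ibrutinib alone in Section 6.1.5: "Five patients discontinued ibrutinib; 3 due to progression and 2 due to adverse events". That is 5 of 31 at a median follow-up of 18.1 months. Treat this as the cumulative risk at 18.1 months and assume a constant hazard:

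- Hazard = −ln(1 − 5/31) / 18.1 = 0.00972 per month.
- Cohort B, 8 weeks (56/30.44 = 1.84 months): p = 1 − exp(−0.00972 × 1.84) = 0.0177.
- Cohort A, 12 weeks including the lead-in (84/30.44 = 2.76 months): p = 1 − exp(−0.00972 × 2.76) = 0.0265.
- Any loss among 12, 1 − (1 − p)^12: 19% in Cohort B and 28% in Cohort A.
- At least one non-responder lost, 1 − (1 − 0.27p)^12: 6% in Cohort B and 8% in Cohort A.

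The factor 0.27 is 1 − 0.73. It assumes that 73% respond and that loss is unrelated to response. If non-responders leave more often, the chance is higher, up to the any-loss figure.

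**Range for a higher loss rate.** At assumed rates of 5%, 10% and 20% per patient, the chance of any loss among 12 is 46%, 72% and 93%. The chance of losing at least one non-responder is 15%, 28% and 49% under the same assumptions.

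**The case against.** The strongest reply is that nothing in Section 16 says early leavers will be excluded. It calculates proportions for each cohort, and the cohorts are 12 patients each. A reader might infer a stated plan to drop patients; the documents do not contain one. This stands as far as it goes: the exclusion is an inference. But the 12 in Section 16 belongs to the toxicity interval, and the evaluability rule, given four times, points the other way. The ambiguity is itself the defect.

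Second, response is secondary in a self-described pilot with no power calculation, response threshold or cohort comparison. Efficacy data are captured for all enrolled patients (Section 15.1), so an all-treated rate can be computed in any case. This also stands, and it limits the weight of the point.

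Two further readings are tempting and should not be pressed:

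- **The rate will be inflated past the historical 73%.** That figure comes from previously treated, rituximab-refractory patients (Sections 1 and 6.1.5). Cohort A also admits treatment-naïve patients, so the comparison is imperfect there. It does not fit Cohort B, which is selected for a plateau on ibrutinib and scored from pre-ibrutinib IgM. Every interval in the table includes 73%, so only the point estimate crosses it.
- **Completion of induction is undefined.** Section 9.3 defines induction as the first 8 weeks of combination treatment, Section 14.1 refers to Weeks 1-8, and Section 12.4.1 says: "If a missed dose occurs during induction, then that dose will not be made up and subjects will remain on schedule". Together these largely settle completion by calendar time. Only a small wording question remains, for example after several missed doses.

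**Conclusion.** The point holds as a gap in specification that should be closed. The only response population defined is conditional on completing induction, and Section 16 names neither a denominator nor an all-treated analysis.

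The size is modest. With 8 of 12 responding, one or two exclusions shift the estimate by about −7 to +13 points. The monotherapy anchor puts the chance of losing a non-responder at about 6% to 8% per cohort. That rests on a constant hazard, a 73% response rate and loss unrelated to response; loss on the combination may be higher. The direction is not fixed, so a reader should not infer that the rate is always overstated.

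The primary toxicity endpoint, the sample size and the stopping rule do not depend on this rule, and there is no hypothesis test on response to be invalidated.

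**What to change.** In Section 16, with matching wording in the synopsis and Sections 1, 14.1 and 14.2:

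- Make the main denominator, for major response and for Cohort B deepening, all patients who received at least one dose of daratumumab. This is the existing toxicity set. Score patients with no documented response as non-responders.
- Report how many Cohort A patients leave during the ibrutinib lead-in, and give a sensitivity rate that counts them as non-responders.
- In Cohort B, tabulate the response category at Cycle 1 Day 1, so that responses already present on ibrutinib are visible.
- Keep the 8-week-completer rate as supportive, with one line stating that completion is judged by time on treatment even if a dose was missed.

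The denominator change is wording only. Table 1 already collects IgM on Day 1 of Cycles 1 and 2, and Section 9.3.5 brings back patients who stop early for toxicity or progression for end-of-treatment procedures, including IgM. The downside is that the headline rate will usually be equal or lower.

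Two neighbouring matters are separate and should be raised on their own: overall response in the synopsis against major response in Sections 1.2 and 16, and the response definitions in Section 14.1 against Appendix C.

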#### 14.2. Time to Event Definitions

**Duration of Response (DoR):** The duration of overall response is measured from the time measurement criteria are met for Minor response or better until the first date that recurrent or progressive disease is objectively documented (taking as reference for progressive disease the smallest IgM measurements recorded since the treatment started).

**Progression-Free Survival (PFS):** PFS is defined as the duration of time from start of treatment to time of progression or death.

**Overall Survival (OS):** OS is defined as the duration of time from start of treatment to time of death or last follow-up.

**Time to Progression (TTP):** TTP is defined as the time to tumor progression as defined in Section 9.1. If the subject has not progressed, then data will be censored at the last study visit at which a tumor assessment was performed.

**Evaluation of toxicity.** All patients will be evaluable for toxicity from the time of their first treatment with Daratumumab.

**Evaluation of response.** All patients included in the study will be assessed for response to treatment if they have completed Cycle 2.

#### 15. Data Reporting / Regulatory Considerations

### **15.1. Data Collection**

The data collection plan for this study is to utilize REDCap to capture all treatment, toxicity, efficacy, and adverse event data for all enrolled patients.

### **15.2. REDCap**

REDCap (Research Electronic Data Capture) is a free data management software system that is fully supported by the Weill-Cornell Medical Center CTSC. It is a tool for the creation of customized, secure data management systems that include Web-based data-entry forms, reporting tools, and a full array of security features including user and group-based privileges, authentication using institution LDAP system, with a full audit trail of data manipulation and export procedures. REDCap is maintained on CTSC-owned servers that are backed up nightly and support encrypted (SSL-based) connections. Nationally, the software is developed, enhanced and supported through a multi-institutional consortium led by the Vanderbilt University CTSA.

### **15.3. Regulatory Considerations**

All protocol amendments and consent form modifications will be made by the Principal Investigator. Janssen will have the opportunity to review and approve the changes prior to submission of these changes to the local IRB and distribution to participating sites.

